This protocol describes the PACE-NODES trial and provides information about procedures for entering participants into this trial. The protocol should not be used as a guide for the treatment of patients outside of this trial.

Every care was taken in the preparation of this protocol, but corrections or amendments may be necessary. Protocol amendments will be circulated to participating sites as they occur, but sites entering patients for the first time are advised to contact ICR-CTSU to confirm they have the most recent version.

**HISTORY OF PROTOCOL AMENDMENTS**

| PROTOCOL VERSION AND DATE | SUMMARY OF CHANGES   |
|---------------------------|--|
| 1.0                       | Original protocol  |
| 2.0                       | Addition of SPRUCE study within a trial
Addition of second primary cancer as a secondary endpoint
Addition of ADT duration $\leq$ 2years as an additional balancing factor
Removal of requirement for consecutive PSA rises to allow for 'PSA bounce'
Imaging timing requirements changed to relate to ADT start rather than randomisation   |
| 3.0                       | Sample size increased from 536 to 1128.
Expected event free rate and effect size reviewed with the effect of increasing sample size.
Site numbers and international site participation details updated.
Strengthened wording around exclusion of patients where the diagnostic MRI showed bowel in close apposition to target volumes.
Confirmation that consent can only be taken by a qualified clinician.
Randomisation procedure updated to reflect current practice.
Lymphedema added as an expected adverse event. |
|                           |  |
|                           |  |
|                           |  |
|                           |  |
|                           |  |
|                           |  |
|                           |  |
|                           |  |

**PACE-NODES TRIAL SUMMARY**

[figure not shown]
|                    |  |
|--------------------|--|
| PROTOCOL TITLE     | PACE-NODES: A phase III randomised trial of 5 fraction prostate SBRT (P-SBRT) versus 5 fraction prostate and pelvic nodal SBRT (PPN-SBRT)   |
| TARGET DISEASE     | 
 
1. Histopathological confirmation of prostate adenocarcinoma with Gleason/ISUP grade group scoring
 
2. Patients planned for of 12-36 months androgen deprivation therapy
 
3. High risk localised prostate cancer as defined by 
 
- Gleason 8-10 (grade groups 4 and 5) and/or
 
- Stage T3a/b or T4 and/or
 
- PSA > 20ng/ml
 
 
 
4. Multi-parametric/bi-parametric MRI of the pelvis- to include at least one functional MRI sequence in addition to T2W imaging, ideally no more than twelve months before starting ADT.
 
5. Radiological staging to exclude metastatic disease (ideally within 3 months prior to starting ADT) with one of the following- PSMA PET-CT, fluciclovine/choline PET-CT, whole-body MRI, bone scan, CT of chest, abdomen and pelvis (imaging method as per local practice/standard of care).
 
 |
| TRIAL OBJECTIVES   | The primary objective is to determine whether PPN-SBRT has superior biochemical/clinical-failure free rate than P-SBRT, in patients with high risk localised prostate cancer.  |
| TRIAL DESIGN       | PACE-NODES is a multicentre phase III randomised controlled trial  |
| TRIAL POPULATION   | Patients with high risk localised prostate cancer, deemed suitable for SBRT radiotherapy and planned for 12 - 36 months androgen deprivation therapy   |
| RECRUITMENT TARGET | The aim is to recruit 1128 participants; 564 into each arm of the study  |
| TRIAL TREATMENT    | 
Patients will be allocated to one of two treatment arms:
 
 
1. Prostate alone SBRT (P-SBRT) to receive 36.25Gy in 5 fractions to the prostate and seminal vesicles
 
2. Prostate and pelvic node SBRT (PPN-SBRT) to receive 36.25Gy in 5 fractions to the prostate and seminal vesicles and 25Gy in 5 fractions to pelvic nodes
 
   |
| PRIMARY ENDPOINT   | Time to biochemical or clinical failure as defined by time from randomisation to the first biochemical failure, local recurrence,  |

|                     |   |
|---------------------|---|
|                     | lymph node/pelvic recurrence, distant metastases, recommencement of androgen deprivation therapy or death due to prostate cancer  |
| SECONDARY ENDPOINTS | 
 
1. Clinical reported acute and late toxicity using CTCAE version 5.0 and RTOG criteria. Focus will be given to GU and GI Grade 2 or higher (G2+) toxicities.
 
2. Metastatic relapse-free survival, prostate cancer-specific survival and overall survival
 
3. PROMs as assessed by IPSS, EPIC-26, EQ-5D and IIEF-5
 
4. Adherence to radiotherapy protocol
 
5. Incidence of second primary cancers
 
   |
| FOLLOW UP           | 
Evaluation during and after treatment will be as follows;
 
 
1. Acute toxicity will be assessed at the final fraction, then 2, 4, 8 and 12 weeks after end of treatment
 
2. Late toxicity will be assessed at 6, 12, 18, 24, 36, 48 and 60 months.
 
3. Quality of life questionnaires will be completed at 4 weeks after treatment and then at 6, 12, 24 and 60 months after the end of treatment.
 
4. PSA (for determination of biochemical failure) will be collected at 6 months following completion of SBRT, then 6-monthly for 5 years.
 
 
Long-term data capture will be pursued through routine data sources.
 |

**TRIAL SCHEMA**

PACE-NODES is a multi-centre, randomised phase III trial which recruits men with high risk localised prostate cancer to receive either 5 fraction prostate SBRT (P-SBRT) or prostate and pelvic node SBRT (PPN-SBRT).

**Figure 1: Trial Schema**

- Toxicity will be assessed using Radiation Therapy Oncology Group (RTOG) grading and the National Cancer Institute Common Terminology Criteria for Adverse Events (CTCAE) version 5.0.
- Patient reported International Prostate Symptom Score (IPSS), Expanded Prostate Index Composite-26 (EPIC-26) and EuroQol-5D (EQ-5D) QoL will be measured at baseline, 4 weeks after treatment and then at 6, 12, 24 and 60 months from the end of radiotherapy. The International Index of Erectile Function 5 (IIEF-5) will be measured at 60 months.
- All participants will be followed up for at least 3.5 years with trial specific follow-up to 5 years.

## 1. INTRODUCTION

### 1.1. Background

Despite the increasing sensitivity of imaging, the presence of undiscovered micrometastatic disease in prostate cancer patients with a higher risk of pelvic nodal involvement [1] increases the risk of recurrence, in particular in patients with high-risk disease. Current clinical trials seek to improve the outcome of this group of patients with an emphasis on maximising the chance of cure, whilst minimising the risk of side effects.

Older trials investigating the prophylactic irradiation of the pelvic nodes have not shown a benefit [2, 3]. However, results are difficult to interpret due to patient selection, inconsistent staging to rule out metastatic disease and outdated radiotherapy techniques. With more conformal delivery methods and image-guided radiotherapy (IGRT), safer dose escalation allows the dose to the organs at risk to be minimised, which may tip the balance in favour of nodal irradiation.

### 1.2. Extreme hypofractionation

With increasing evidence for a low alpha-beta ratio for prostate cancer [4], several large randomised trials, including the CHHiP trial, have demonstrated that moderate hypofractionation achieves similar biochemical control compared to conventional treatment, without an increase in gastrointestinal (GI) or genitourinary (GU) toxicity [5-7]. These have redefined standard of care for radical treatment in localised prostate cancer.

Extreme hypofractionated schedules, delivering doses of >6 Gray (Gy) per fraction (f), have similar side-effects to moderate hypofractionation and may improve outcome [1, 8]. They have additional benefits of being more patient-friendly and reducing the burden on radiotherapy departments, with an associated reduction in healthcare costs [9].

PACE-B, a phase III randomised clinical trial of prostate stereotactic body radiotherapy (SBRT) in men with low and intermediate risk prostate cancer, compared 5 fraction SBRT at a dose of 36.25Gy against standard conventional or moderately fractionated schedules. Acute toxicity data confirms 5-fraction SBRT is safe compared to the current 20 fraction standard of care [1]. In the standard and SBRT groups, the proportion of patients with acute RTOG  $\geq$  grade 2 GI toxicity was 12% and 10% respectively and acute RTOG  $\geq$  grade 2 GU toxicity was 27% and 23% respectively. These toxicity rates are lower than those seen in the CHHiP trial [3], likely to be due to a combination of mandated IGRT, smaller margins and more conformal planning techniques within the PACE-B trial. Recent late toxicity data from PACE-B demonstrates a higher cumulative incidence (to 27 months) of Gr2+ CTCAE GU toxicity with SBRT compared with the standard of care group (32.2% vs 19.8%), and a similar cumulative incidence of Gr2+ CTCAE GI toxicity (12.5% vs 12.3%) [10]. Toxicity across both groups overall was low. HYPO-RT-PC, which also included 11% high risk patients, compared conventional/moderately fractionated treatment with extreme hypofractionated radiotherapy (EHFRT) schedules delivering >6Gy/f, demonstrating acceptable acute toxicity [1, 8]. Low rates of late toxicity were also reported with EHFRT (2-year cumulative incidence of RTOG Gr2+ GU and GI toxicity were 13% and 6% respectively, compared with 9% and 5% with conventional fractionation), and the trial demonstrated non-inferiority of EHFRT compared to conventionally fractionated treatment in terms of biochemical and clinical failure-free survival up to 5 years post-treatment.

There is more limited data available for higher risk patients, with the ongoing PACE-C trial randomising higher risk patients (up to 12 months ADT) to 20 fraction prostate radiotherapy or 5 fraction prostate SBRT.

Assessing safety in this group is paramount to ensure that treatment remains safe and effective with more advanced disease and larger volume seminal vesicle inclusion. However, PACE-NODES seeks to demonstrate the efficacy and safety in an even higher risk group, with the inclusion of Gleason 9 and T3b/T4 staged disease.

### **1.3. Pelvic nodal radiotherapy**

Radiotherapy to the prostate and lymph nodes gives acceptable toxicity but is normally given over several weeks, using a moderately hypofractionated regime. The phase III PIVOTALboost trial is comparing 20 fraction prostate and pelvis radiotherapy to prostate alone, with or without a boost to the dominant intraprostatic lesion. The preceding multi-centre phase II PIVOTAL study demonstrated intensity modulated radiotherapy (IMRT) to the prostate and pelvic nodes (60Gy over 7.5 weeks) is safe with low additional toxicity compared to prostate radiotherapy [5]. A smaller single centre phase I/II study has reported acceptable toxicity rates with pelvic nodal radiotherapy given over four weeks, with cumulative 2 year RTOG > grade 2 GI and GU toxicity of 16.4% and 4.8% respectively [7].

In January 2021, the 224 patient phase III randomised POP-RT trial [10] reported improved outcome with the addition of whole pelvic radiotherapy, with a 5 year biochemical failure-free survival of 95.0% versus 81.2% for prostate-only radiotherapy giving a hazard ratio of 0.23 for biochemical failure (95% CI: 0.10 to 0.52,  $p=0.0001$ ) using 25 fractions. The hazard ratio for disease-free survival was 0.4 (95% CI, 0.22 to 0.73,  $p=0.002$ ). Patients were eligible for this study with a risk of nodal involvement of at least 20%, as determined using the Roach formula [11] with 46.8% of patients having at least T3b disease. This is the first randomised evidence to demonstrate a benefit for pelvic nodal radiation and of relevance, approximately 80% of patients underwent PSMA PET CT imaging for staging.

With the movement towards extreme hypofractionation, several smaller, early phase trials have treated high risk prostate cancer with prostate and pelvic nodal SBRT, including FASTR [12], FASTR-2 [13], SATURN [14] and PRIME [15]. The SPORT trial (NCT03253978) is a single-centre study randomising 30 patients with unfavourable intermediate and high risk localised prostate cancer to prostate alone 36.25Gy in 5f, or prostate and pelvic node SBRT, with additional 25Gy to the pelvic nodes. This demonstrated that radiotherapy to the prostate and lymph glands in five visits was technically feasible with acceptable side effects [16]. We now need to test SBRT to the prostate and pelvic lymph nodes in high risk prostate cancer at multiple centres.

With this preliminary data on pelvic nodal SBRT, the encouraging results for nodal radiotherapy from POP-RT in the 25 fraction setting and UK trials of both 20 fraction prostate and pelvic lymph node radiotherapy and 5 fraction prostate SBRT anticipated to report efficacy results within the next 5 years, PACE-NODES is the natural next step.

### **1.4. Description of Population**

Patients with newly diagnosed high risk localised prostate cancer, deemed suitable for SBRT and planned for a minimum of 12 months androgen deprivation therapy.

### **1.5. Study Rationale**

With increasing evidence for prostate SBRT in low and intermediate risk localised prostate cancer, and the increased risk of micrometastatic nodal disease in men with high risk localised prostate cancer, PACE-NODES

seeks to assess the efficacy and safety of 5 fraction SBRT to the prostate, with or without pelvic nodes, in this group of patients.

## 2. TRIAL OBJECTIVES

### 2.1. Primary Objective

To determine whether 5 fraction prostate and pelvic node SBRT (PPN-SBRT) has a superior biochemical/clinical-failure free rate (reduces the risk of biochemical or clinical failure by 40% or more) than 5 fraction prostate SBRT (P-SBRT), in patients with high risk localised prostate cancer.

### 2.2. Secondary Objectives

The trial has the following secondary objectives:

- to assess acute and late GI and GU toxicity with SBRT and PPN-SBRT; and, specifically, to rule out a doubling in the cumulative rate of late gastrointestinal (GI) toxicity (occurring between 6 and 24 months after treatment) with PPN-SBRT when compared to P-SBRT.
- to assess patient reported outcome measures (PROMs) of bowel, urinary and late erectile dysfunction with the two treatments.
- to assess efficacy of the two treatment approaches in terms of subsequent occurrence of metastatic disease and (prostate cancer) deaths.
- to demonstrate feasibility of PPN-SBRT with respect to radiotherapy planning and delivery (adherence to pre-specified dose constraints) in a multi-centre setting.

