### **12.1.3. Power for secondary toxicity analysis**

This number of patients also gives adequate power for secondary toxicity comparisons, aimed at demonstrating “non-inferiority” of PPN-SBRT in terms of late gastrointestinal toxicity (CTCAE grade 2+), as follows:

Assuming a 92% evaluable rate (based on expected recurrence-free rate at 2 years and allowing for some loss to follow-up), 1038 patients would be evaluable for toxicity comparison up to 2 years. Assuming a P-SBRT toxicity rate of 13% (based on data from PACE-B [19]), the trial will have more than 85% power, with a one-sided 5% significance level, to rule out a PPN-SBRT toxicity rate of >19%, i.e. accepting an increase of up to 6% worse.

If toxicity rates are lower we will still have very good power (at least 90%) to rule out a doubling in toxicity. This relative non-inferiority margin (“a doubling”) is informed by POP-RT where the cumulative late RTOG grade 2+ gastrointestinal toxicity was 6.5% for WPRT and 3.8% for PORT [20]. Unless absolute rates are very low, we will have good power (>80%) to rule out smaller relative effects (E.g. with a 10% P-SBRT toxicity rate, we would have >80% power to rule out a 50% increase, to 15%, with PPN-SBRT).

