### **12.3.2. Secondary endpoints**

A key secondary endpoint is late gastrointestinal (GI) toxicity, grade  $\geq 2$  (CTCAE, clinician assessed).

Assessment of GI toxicity is particularly important with PPN-SBRT given the increased bowel dose compared to prostate alone radiotherapy. CTCAE is a recognised standard used in other relevant trials. Given the potential for discrepancies between clinician and patient reported toxicity [21], patient reported outcomes measures (PROMs) as a measure of the direct impact on patient quality of life [22] will provide complementary information to clinician assessed toxicity.

Other secondary endpoints include:

- Time from randomisation to first of: recommencement of androgen deprivation therapy; biochemical failure; loco-regional recurrence (recurrence in the prostate and/or pelvic lymph nodes).
- Metastatic relapse-free survival, defined as time from randomisation to distant metastases or death from prostate cancer.
- Prostate cancer-specific survival, defined as time from randomisation to death due to prostate cancer.
- Overall survival, defined as time from randomisation to death from any cause.
- Acute toxicity, occurring within the first 12 weeks of follow-up (CTCAE and RTOG), with a focus on GI and GU toxicity, grade  $\geq 2$ .
- Late toxicity, reported from the 6 month visit onwards (CTCAE and RTOG), with a focus on GI and GU toxicity, grade  $\geq 2$ .
- Quality of life measured using the following questionnaires: the International Prostate Symptom Score (IPSS), the 5-item version of the International Index of Erectile Function (IIEF-5), the short form Expanded Prostate Index Composite-26 (EPIC-26) and the EQ-5D-5L (see section 19.2 for further details).

- Radiotherapy planning and delivery data (PTV for prostate and pelvic nodes; adherence to dose constraints; and deviations from allocated treatment arm) to demonstrate feasibility.
- Second primary cancers occurring during trial follow-up.

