#### **12.4. Statistical Analysis Plan**

All statistical analysis will be conducted by the ICR-CTSU at The Institute of Cancer Research (or in collaboration with the statistical team at ICR-CTSU). Analysis methods are outlined here, in brief. Full details will be specified in a Statistical Analysis Plan in accordance with ICR-CTSU Standard Operating Procedures.

The timing of the principal efficacy analysis is planned to be event-driven, with the required number of events expected to be achieved when all participants have a minimum of approximately 3.5 years follow-up in the trial. The Independent Data Monitoring Committee (IDMC) will monitor the accumulation of follow-up data and primary endpoint events in the trial and will advise on when the dataset is sufficiently mature for analysis.

Efficacy analyses, including the primary endpoint comparison, will include all randomised participants according to allocated treatment arm (intention-to-treat). Toxicity analyses will be performed on a per protocol analysis set, to be defined within the Statistical Analysis Plan.

The primary endpoint, as well as other time-to-event endpoints, will be presented by treatment arm using Kaplan-Meier curves; estimated 5-year event rates will be given along with 95% confidence intervals. Hazard ratios (presented with 95% confidence intervals and p-values) will be estimated from Cox proportional hazards model with adjustment for minimisation factors. Proportional hazards assumptions will be checked and, if violated, appropriate alternative methods will be applied.

Acute toxicity data will be analysed when all participants have reached the 12-week visit. Late toxicity data will be analysed when all participants have reached the 2-year visit (or been lost to follow-up/withdrawn prior to this time). Acute and late toxicity data will be summarised as grade and grade  $\geq 2$  frequencies and percentages at each time point. Worst grade adverse events occurring within each period (acute and late) will also be summarised. For each period, the proportion experiencing GI and GU toxicity (grade  $\geq 2$ ) will be presented along with the difference in proportions with 90% confidence intervals (reflecting a one-sided 5% significance level). The relative difference between treatment groups will be estimated using logistic regression models; odds ratios with 90% confidence intervals will be presented.

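### Late GI toxicity has two non-inferiority margins, a doubling in 2.2 and +6 percentage points in 12.1.3, with no rule for which governs; the doubling has no estimate on its own scale, and the analysis window is looser than the objective's

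*Protocol*

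**What the plan says.** - **Protocol 2.2 (Secondary Objectives)** gives one criterion, without condition: "to rule out a doubling in the cumulative rate of late gastrointestinal (GI) toxicity (occurring between 6 and 24 months after treatment".
- **Protocol 12.1.3 (power for toxicity)** assumes 13% in the P-SBRT arm and 1038 evaluable patients. It claims more than 85% power, one-sided 5%, "to rule out a PPN-SBRT toxicity rate of >19%, i.e. accepting an increase of up to 6% worse".
- The same section continues: "If toxicity rates are lower we will still have very good power (at least 90%) to rule out a doubling in toxicity". It calls the doubling a relative non-inferiority margin, and says that this margin "is informed by POP-RT where the cumulative late RTOG grade 2+ gastrointestinal toxicity was 6.5% for WPRT and 3.8% for PORT". A third effect size appears as an illustration: "with a 10% P-SBRT toxicity rate, we would have >80% power to rule out a 50% increase, to 15%, with PPN-SBRT".
- **Protocol 12.4** plans, for each toxicity period, a difference in proportions with a 90% interval tied to the one-sided 5% level. For the relative effect, logistic regression is used and "odds ratios with 90% confidence intervals will be presented".
- **Protocol 12.3.2** names late grade 2+ GI toxicity (CTCAE) as a key secondary endpoint without giving it a window. In its list of other endpoints it defines "Late toxicity, reported from the 6 month visit onwards".

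**The concern.** A non-inferiority conclusion depends on its margin. Here the objective and the power statement use different margins on different scales, and no sentence ranks them or says at what control rate one gives way to the other. A result could then meet the objective in 2.2 while failing the margin on which 12.1.3 bases its claim, or the reverse.

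This matters because 12.1.1 justifies the target hazard ratio as enough to offset a likely rise in toxicity, and 12.5 allows the late toxicity results to be published before the efficacy analysis. The tolerability statement will therefore be read on its own.

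Two smaller mismatches follow. The criterion in 2.2 is a ratio of rates, but the planned relative estimate is an odds ratio. The objective also stops at 24 months, but the late period as defined does not.

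**Working it through.** **Inputs.** Evaluable: 0.92 × 1128 = 1037.8, stated as 1038 (12.1.3). With 1:1 allocation (12.1.1) this is 519 per arm. Control rate 13%; one-sided 5%, so z = 1.645 and a 90% interval.

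**1. The plan's own power.** Risk-difference scale, equal true rates of 13%, margin 0.06:

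- SE = √(2 × 0.13 × 0.87 / 519) = 0.02088
- Power = Φ(0.06/0.02088 − 1.645) = Φ(1.229) = 89.0%

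This agrees with the stated figure of more than 85%. The 10% to 15% illustration gives 85.1% on the same scale, which agrees with the stated figure of more than 80%.

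**2. What each margin permits.** A doubling equals +6 points only where 2p = p + 0.06, so p = 6%.

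| Control rate | Doubling | +6 points | Risk ratio implied by +6 |
|---|---|---|---|
| 3.8% | 7.6% | 9.8% | 2.58 |
| 6% | 12% | 12% | 2.00 |
| 13% | 26% | 19% | 1.46 |

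**3. Upper 90% limits.**

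- Difference: (p₂ − p₁) + 1.645 √[p₁(1−p₁)/519 + p₂(1−p₂)/519]
- Risk ratio: (p₂/p₁) × exp{1.645 √[1/a + 1/b − 2/519]}, with a and b the event counts

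With exactly 13% observed in control, the largest PPN-SBRT rate that passes is 15.4% under the 6-point rule and 20.6% under risk ratio < 2.

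- *67/519 versus 88/519 (12.9% v 17.0%).* Difference limit: 0.0405 + 1.645 × 0.0221 = 7.7 points, which fails +6. Risk-ratio limit: 1.313 × exp(1.645 × 0.1498) = 1.68, which rules out a doubling.
- *20/519 versus 34/519 (3.9% v 6.6%).* Difference limit: 0.0270 + 1.645 × 0.0138 = 5.0 points, which passes +6. Risk-ratio limit: 1.70 × exp(1.645 × 0.2749) = 2.67, which does not rule out a doubling.

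**4. How often the rules disagree** (400,000 simulated trials per row, 519 per arm).

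| True rates | Passes +6 | Rules out doubling | Rules disagree |
|---|---|---|---|
| 13% v 17% | 23% | 87% | 64% |
| 13% v 19% | 5% | 69% | 64% |
| 3.8% v 6.5% | 77% | 14% | 63% |

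**5. Scale of the relative estimate.** At 13%, a doubling corresponds to an odds ratio of (0.26/0.74)/(0.13/0.87) = 2.35. At 3.8% it is 2.08. The odds ratio that represents a doubling therefore moves with the control rate.

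**6. Power for a doubling at low rates** (equal true rates).

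- As a fixed difference at 3.8%: Φ(0.038/√(2 × 0.038 × 0.962/519) − 1.645) = 94.0%. The claim of at least 90% holds down to a control rate of about 3.2%.
- As a risk ratio: Φ(ln 2/√[2(1−p)/(519p)] − 1.645) = 71.7% at 3.8% and 88.0% at 6%. Exact binomial calculation gives about 71% and 87%. The 90% claim holds only from about 6.4% upwards.

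**7. Window.** Section 12.4 analyses late toxicity once everyone has reached the 2-year visit. Recruitment spans 37 months (12.1.1), so the earliest participants may by then have about 37 + 24 = 61 months in the trial, including their 36- and 48-month visits. A worst-grade summary over a late period open from 6 months would count events that 2.2 excludes and that 12.1.3, which speaks of a comparison up to 2 years, did not plan for.

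**The case against.** Section 12.1.3 can fairly be read as scenario-based: an absolute margin at the expected 13%, a doubling if rates turn out lower, and the 50% increase only as an example. At 13% the margins are nested, so any result that passes +6 points also rules out a doubling. On this view there is a strict powered margin above a looser objective, and the analysis plan, which is not shown, may state the hierarchy. This softens the conflict but does not remove it. No switching rate is given, 2.2 states the doubling without condition, and at low rates the stricter margin changes sides. An analysis plan could settle the matter only by overriding or qualifying one of the two sections.

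A reader might infer three stronger points that the protocol does not support:

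- *That the analysis fits neither margin.* The difference in proportions in 12.4 is on exactly the scale of the 6-point margin. Only the doubling lacks a matching estimate.
- *That an odds ratio below 2 is a third criterion.* No odds-ratio limit appears anywhere in the protocol.
- *That the power is misstated.* The figures reproduce on the difference scale. The low-rate claim falls short only if the doubling is tested as a risk ratio.

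On the window, the open-ended definition stands in the list of other endpoints and not beside the key endpoint. But 12.3.2 gives the key endpoint no window of its own and 12.4 analyses late toxicity by period, so the ambiguity remains in this smaller form.

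**Conclusion.** The point holds as a conflict between stated criteria. At the planning rate, observed PPN-SBRT rates from about 15.5% to 20.5% would meet the objective in 2.2 and fail the margin in 12.1.3. Near 4% versus 6.5% the reverse occurs. For true rates in these regions the two rules disagree in roughly 63% to 64% of trials.

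The figures assume 519 evaluable per arm, unadjusted Wald-type limits, and the doubling judged as a risk ratio. Other interval methods would shift the limits slightly and leave the gap in place.

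Severity is moderate. Late GI toxicity is a key secondary endpoint, and no passage makes it the sole test of whether PPN-SBRT is acceptable. It would go too far to say that the conclusion is free to be chosen once the data are in, because an analysis plan may yet fix the rule. The protocol text itself does not.

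**What to change.** Before late toxicity data are seen:

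1. **Name one governing margin and scale in 2.2 and 12.1.3.** The natural choice is that the upper 90% limit of the risk difference lies below 6 points. It is already powered (89%), 12.4 already plans the estimate, and at the planning rate it also rules out a doubling. The objective in 2.2 would then be reworded, because below a 6% control rate a 6-point margin permits more than a doubling. How much excess toxicity is tolerable remains the sponsor's judgement.
2. **If the doubling is kept for low rates, state the switching rule and the scale.** Say whether the switch depends on the observed or the expected control rate. If the scale is the risk ratio, restate the claim of at least 90% power: it is about 71% at a 3.8% control rate and 87% at 6%.
3. **In 12.4, report a risk ratio with a 90% interval** for the relative effect.
4. **In 12.3.2 and 12.4, restrict the key comparison to the 6–24 month visits.** Later toxicity can be summarised separately.

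The cost is wording in four sections and, if the doubling is retained as a risk ratio, a less favourable stated power at low rates. The sample size does not change.
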